5.1 Intraoperative Monitoring

5.1.1 - Patient in both groups will have arterial lines placed per current procedural policy. As is currently practiced hemodynamic and physiologic parameters will be monitored. If available, LiDCO-Rapid technology will be used to track other hemodynamic parameters during the duration of the procedure. Perioperative fluids, vasoactive medication administration, urine output, and blood product transfusions will be documented as per current guidelines. Central venous pressure will be recorded in those patients that have central venous catheters.

5.2 Postoperative Monitoring

5.2.1 - After surgery, patients in both groups will be initially admitted to the PACU and subsequent disposition to either intensive care unit, overnight recovery suite, or general surgical floor dictated by patient status and the anesthesia and primary surgical team discretion. Patient monitoring in ICU, overnight recovery, or floor will be per current practice.

5.2.2 - 15cc of blood will be drawn intraoperatively prior to anesthesia induction and daily every other day (POD# 1, 3, 5) postoperatively with other standard postoperative tests, for laboratory correlates of analgesic mediated immune function. 5cc of blood will be drawn into purple top (ETDA) tubes and 5cc will be drawn into 2 green top (Heparinized) tubes. All blood samples will be kept on ice for transport (up to 8hrs). After blood draw (performed at same time as routine daily postoperative labs) samples will be sent to laboratory Y6.25 (pager -[name]). Laboratory personnel involved include [name] and [name]. For cell separation a Ficoll gradient technique will be used and for plasma collection, we will spin each EDTA sample for 10 min at

2000 rpm at 4 degrees C. Samples will be stored until processing at -80 degrees C in laboratory freezer with samples de-identified for confidentiality. These correlative studies are optional however will not require additional blood draws to the patient as they are being drawn simultaneously to the routine perioperative blood draws.

6. Postoperative Assessments

6.1 Postoperative Epidural Assessment (TEA only)

6.1.1 - The Acute Pain Service will monitor epidural site daily for evidence of hematoma, cellulitis, abscess, CSF leak, and malfunction as is current practice.

6.2 Postoperative Motor Block Assessment (TEA only)

6.2.1 - Motor status will be assessed approximately every nursing shift and before ambulation as is current practice (Appendix C).

6.3 Postoperative Sensory Block Assessment (TEA only)

6.3.1 - Sensory status will be assessed approximately every nursing shift to ensure adequate epidural function and that block is within expected dermatome levels as is current practice (Appendix D).

6.4 Postoperative Sedation Assessment (TEA and IVPCA)

6.4.1 - Sedation will be assessed using Richmond Agitation Sedation Scale (RASS) approximately every nursing shift per current practice (Appendix E).

6.5 Postoperative Pain Assessment (Both TEA and IVPCA Groups)

6.5.1 - Pain scores will be assessed in both groups with a Numeric/Visual Pain Scale (0-10) at various time points in the clinical record per current inpatient policies (Appendix F). Beginning in the PACU after surgery, pain will be assessed by nursing staff approximately every hour per current practice until disposition to inpatient care units. In the overnight recovery suite and general floor pain will be assessed by nursing staff approximately every 4 hours per current practice. In the SICU pain will be assessed by nursing staff approximately every hour per current practice. The pain assessments that are being used for analysis are average pain scores within first 6hrs postop, the next 18hrs, and each 24hr period thereafter. The pain scores for each 24 hour period after this will be averaged (as many as are collected). Pain will re-assessed by nursing staff approximately 1 hour after every analgesic intervention per current practice on all nursing floors. All dosing alterations, changes, and total narcotic/analgesic use will be documented in the clinical record per current practice.

6.5.2 - The Acute Pain Service team/nurse will assess all patients in both groups (TEA and IVPKA). Therapeutic analgesic interventions in the TEA group will be per discretion of the Acute Pain Service per current practice. Therapeutic interventions in the IVPKA group will be per discretion of the primary surgical team per current practice and the primary surgical team will be blinded to the Acute Pain Service assessment of patients in IVPKA group.

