4.1 IVPCA

4.1.1 - Immediately following surgery, the OR Anesthesia team will titrate intravenous narcotics in the PACU for pain down to an acceptable level prior to initiating IVPCA. All patients assigned to IVPCA group will be started on intravenous patient-controlled analgesia protocol according to current institutional policy following surgical procedures. All patients will be given hydromorphone as the opioid of choice per current practice, unless there are contraindications. Fentanyl or Morphine will be secondary alternatives. Initial recommended starting doses are: no basal rate, 0.2mg every 10 minutes demand dosing, and a 0.5mg nursing bolus every 1 hour as needed for additional pain control (Appendix A). Adjunctive use oral, rectal, or intravenous non-narcotic analgesics (acetaminophen, non-steroidals, etc.) will be utilized at the discretion of the Primary Surgical Team.

4.1.2 - Patients whose IVPCA's are not functioning or not providing adequate analgesia will be considered for possible postoperative placement of TEA (coagulation studies permitting) as an alternative analgesic regimen (patient crossover).

4.1.3 - Further drug information can be found in the MDACC formulary and the FDA approved package inserts of the medications as they are all commercially available.

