4.2 TEA

4.2.1 - All patients assigned to TEA will have thoracic epidurals placed preoperatively in either the holding area or in the operating room according to current institutional protocol. Epidural catheters will be placed between the Thoracic 5th-Thoracic 10th interspinous levels using standard technique according to institutional practices. All epidural catheters will be tested for correct placement and level of block documented and secured as is currently practiced. The epidural will be initially dosed according to current practices with hydromorphone (10 mcg/kg for pts 65 yrs or younger and 5 mcg/kg for pts > 65yrs) after induction of anesthesia. Standard epidural solutions are: Hydromorphone (10 mcg/ml for pts 65yrs or younger and 5 mcg/ml for pts > 65yrs) and Bupivacaine (0.075%) at 10 ml/hr continuous infusion and a 3ml every 10 minutes demand dosing, and a 5ml every 3 hours clinician bolus as needed for additional pain control (Appendix B). Fentanyl with Bupivacaine

will be secondary alternatives. Adjunctive use of oral, rectal, or intravenous non-narcotic analgesics (acetaminophen, non-steriodals, etc.) will be utilized at the discretion of Acute Pain Service and/or Primary Surgical Team. Epidural catheters will remain in place a maximum of 7 days postoperatively. Epidural catheters will be removed once patients are successfully tolerating a full diet or tube feeds and are transitioned to oral/enteral analgesics. Indwelling urinary catheters will be removed after TEA removal per current policy.

4.2.2 - Patients whose TEA's are not functioning or not providing adequate analgesia will be considered for IVPCA as an alternative analgesic regimen (patient crossover).

4.2.3 - Further drug information can be found in the MDACC formulary and the FDA approved package inserts of the medications as they are all commercially available.

5. Treatment Plan – Perioperative Monitoring

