assays will be from optional blood collected as described in 5.2.2.

7.2.4 - Pain score at each time point

- Mean pain scores at various time points will be compared between groups (TEA vs. IVPCA). There will be 6 specific timepoints that will be used for secondary analysis as each timepoint will be an independent measure and may differ between groups dependent on duration from surgery as was found in previous studies: 1). mean pain scores compared between groups at 6 hrs postop; 2). mean pain scores compared between groups for subsequent 18hrs postop; 3). mean pain scores compared between groups over 24hrs on postop day #2; 4). mean pain scores compared between groups over 24hrs on postop day #3; 5). mean pain scores compared between groups over 24hrs on postop day #4; and 6). mean pain scores compared between groups over 24hrs on postop day #5.

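### The six secondary pain-window scores average however many values were charted, so the TEA versus IVPCA comparisons are open to bias if charting frequency differs by arm

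*Combined protocol and SAP*

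**What the plan says.** Section 6.5.1 defines the windows: "The pain assessments that are being used for analysis are average pain scores within first 6hrs postop, the next 18hrs, and each 24hr period thereafter". For the 24-hour windows it adds: "The pain scores for each 24 hour period after this will be averaged (as many as are collected". Section 8.1 repeats the averaging for the 6-hour, 18-hour and later windows and applies a two-sample t-test or Wilcoxon test at each. Section 7.2.4 lists the six comparisons as secondary.

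How often a score is charted depends on where the patient is and what has been given:

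- PACU: "pain will be assessed by nursing staff approximately every hour per current practice until disposition to inpatient care units".
- Overnight recovery and floor: "In the overnight recovery suite and general floor pain will be assessed by nursing staff approximately every 4 hours per current practice".
- SICU: about hourly (6.5.1).
- After treatment: "Pain will re-assessed by nursing staff approximately 1 hour after every analgesic intervention per current practice on all nursing floors".

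Ward after the PACU follows patient status and team discretion (5.2.1). Analgesic interventions are directed by the Acute Pain Service in the TEA arm and by the primary surgical team in the IVPCA arm (6.5.2).

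The primary pain endpoint is handled differently. It is a trapezoidal AUC over 48 hours (7.1.1, 8.1), which weights each score by the time it represents. No section weights the window scores by time, limits them to scheduled scores, or adjusts for ward.

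**The concern.** A plain average gives each charted value the same weight. An hour in the SICU then counts about four times as much as an hour on the floor (24 scores per day against 6), and hours around an intervention count more than quiet hours. Two patients with the same pain curve can receive different window scores because of where they were nursed and how often they were treated. Both are settled after randomization, in an unblinded trial, so charting could differ between arms and add a difference that is not a difference in pain.

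The plan would also summarize the same data under two rules. The first three windows (6 + 18 + 24 = 48 hours) cover exactly the primary period, so the window results need not reconcile with the primary AUC.

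**Working it through.** **The plan's own figure.** Inputs from section 8.2: difference 1, SD 1.5, 105 versus 35 evaluable, two-sided 0.05. Standard error = 1.5 × √(1/105 + 1/35) = 0.293, so the standardized difference is 1/0.293 = 3.42. Power is 92.7% by the normal approximation and 92.4% by the noncentral t with 138 df, which reproduces the stated 92%. Charting frequency does not enter this calculation.

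**One patient, straight-line decline (assumed).** Pain at hour t is 6 − t/8, falling from 6 to 3 over 24 hours. The plain mean equals 6 minus one eighth of the mean charting time.

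- Whole 24 hours, hourly from 0 to 12, then 16, 20, 24: times sum to 78 + 60 = 138 over 16 scores, mean 8.625, plain mean 4.92. The true mean is 4.50, so the gap is +0.42. This is not one of the plan's windows.
- 6-24 h window, true mean 6 − 15/8 = 4.125. Hourly from 6 to 12, then 16, 20, 24: (63 + 60)/10 = 12.3, plain mean 4.46, gap +0.34.
- Same window, hourly charting ending at 6, then 10, 14, 18, 22: 70/5 = 14, plain mean 4.25, gap +0.125.

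The last two count the hour-6 score in the later window. If it belongs to the first window, they become 117/9 = 13 (4.375, gap +0.25) and 64/4 = 16 (4.00, gap −0.125). The plan does not say which window an edge score belongs to.

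**One patient, step profile (assumed).** Pain is 6 for 8 hours, then 4 for 16 hours.

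- Hourly for 8 hours, then 4-hourly: (8 × 6 + 4 × 4)/12 = 5.33.
- 4-hourly throughout: (2 × 6 + 4 × 4)/6 = 4.67.
- Time-weighted: (8 × 6 + 16 × 4)/24 = 4.67.

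The gap is 0.67. Between arms it shrinks in proportion to the difference in the share of patients charted hourly: 0.67 × 0.20 = 0.13 for a 20-point difference, 0.67 × 0.40 = 0.27 for 40 points.

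**Between arms, no true difference (simulation).** 105 versus 35 patients, one 24-hour window, 1,000 runs per row. Assumed: autocorrelated pain averaging about 4 and drifting down; 4-hourly charting; SICU patients charted hourly for 12 hours first; and extra score pairs (at a request and 1 hour later) placed more often at high pain. The SICU share is 20% in both arms in the first four rows. Bias is TEA minus IVPCA, so a negative value favors TEA.

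| Assumed charting, TEA vs IVPCA | Bias, plain mean | Rejection, plain mean | Rejection, time-weighted |
|---|---|---|---|
| 2 vs 2 pairs per day | +0.02 | 4.6% | 4.8% |
| 1 vs 3 pairs | −0.18 | 9.1% | 4.0% |
| 1 vs 5 pairs | −0.30 | 17.3% | 5.8% |
| 3 vs 1 pairs | +0.19 | 9.6% | 4.4% |
| 2 vs 2 pairs, SICU 40% vs 20% | +0.03 | 5.2% | 5.1% |
| 2 vs 2 pairs, SICU 60% vs 20% | +0.08 | 6.1% | 5.0% |

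Twice the simulation standard error at 5% is 2 × √(0.05 × 0.95/1000) = 1.4 points, so the rejection rates in the two SICU rows cannot be told apart from 5%. The time-weighted column uses the fully observed curve; trapezoids on sparse scores would do somewhat less well. In a separate simulation that applied trapezoids to charted scores, the within-patient gap fell from +0.19 to +0.37 (plain) to +0.03 to +0.09.

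**The case against.** A reader might infer that the comparisons are biased, and biased toward TEA, because the IVPCA starting orders allow "a 0.5mg nursing bolus every 1 hour as needed for additional pain control" while the TEA orders allow "a 5ml every 3 hours clinician bolus as needed for additional pain control". The documents do not support that, for four reasons.

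- Both intervals are limits on as-needed dosing, not rates of use. Appendix B adds patient demand doses and an optional intravenous breakthrough line for TEA, and 6.5.1 does not define an analgesic intervention. Counts per arm cannot be derived.
- The background in 2.7 reports more ICU admissions and more changes of analgesic with epidural in a retrospective pancreatic series. If that recurred here, it would raise charting in the TEA arm.
- The only event-driven score that 6.5.1 describes comes about 1 hour after an intervention, when pain may have eased. With only that recheck and an assumed relief of 1 to 2 points, a within-patient check gave gaps of −0.11 to +0.07; with no relief, +0.16 to +0.21. Gaps of +0.19 to +0.41 appeared only when a score at the moment of high pain was added, which the documents do not state. The simulated score pairs above share that assumption.
- Equal charting in both arms, even when tied to pain, gave essentially no between-arm bias. A within-patient gap must not be set directly against the 1-point design difference.

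It is also fair to say that the sentence on averaging as many scores as are collected covers only the 24-hour windows, that a plain average is the natural reading but is not spelled out, and that a patient in the SICU for a whole window is charted evenly on schedule. The averaging in 8.1 does, however, cover all six windows, and no section gives another weighting. These points remove the claim of a demonstrated, one-directional bias. They leave standing a summary that depends on charting frequency.

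**Conclusion.** The point holds in a limited form. Each secondary window score depends on how often the patient was charted as well as on the pain. In the 6-24 h window the assumed straight-line decline gives +0.13 to +0.34 points for one patient, with sign and size also sensitive to the treatment of the edge score. The TEA versus IVPCA comparisons are open to bias if charting intensity, or its link with pain, differs by arm. Under assumed imbalances in intervention-linked scores, rejection with no true difference rose to between 9% and 17%; SICU imbalance alone did little. No arm-level size or direction can be stated, because the documents give no charting, rescue or SICU figures by arm. The simulation covers only the case of no true difference.

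The six comparisons are secondary. The primary trapezoidal AUC, the 92% power and the enrollment of 200 are unaffected. Section 8.1 does not say whether the mixed model uses raw scores or window means, so the point cannot be extended to it. An unknown direction is a reason to settle the rule before the data are analyzed.

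**What to change.** In 6.5.1, 7.2.4 and 8.1, define each window score as the trapezoidal AUC of the charted scores over the window divided by the window length in hours, interpolating at the window edges. This is the primary endpoint's rule applied to a shorter interval, and it settles which window an edge score belongs to. Use these scores in the t-tests or Wilcoxon tests at the six time points. Keep the plain average as a sensitivity analysis, and report the number of scores per patient in each window by arm and ward, so that a reader can see whether charting differed.

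The cost is a few sentences and minor programming. The charted times are already needed for the primary AUC, and the sample size does not change. Some error remains where charting is sparse, because a trapezoid across a 4-hour gap assumes that pain changed in a straight line between scores.

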6.6 Postoperative Quality of Life and Recovery Questionnaires

- Several postoperative Quality of Life and Surgical Recovery instruments will be filled out by participating patients in both groups. Please refer to 7.2.2 for details.

7. Measured Outcomes (TEA and IVPKA)

7.1 Primary Endpoints

7.1.1 - Pain scores (Numeric/Visual Pain Scale)

Pain score AUC within the first 48 hours will be used as the primary endpoint. The AUC for each patient will be computed using the trapezoidal method using the pain score versus time curve. The mean AUC pain scores within the first 48 hours will be compared between TEA and IVPKA groups for the primary analysis.

7.1.2 - Quality of Life

- Patients will complete a validated SF-8, Acute Recall QOL survey (preoperatively and then at approximately 24hrs after surgery) (Appendix G)
- Patients will complete a validated SF-36v2, Acute Recall QOL survey (preoperatively and then prior to discharge or at approximately 1 week after surgery – whichever is first) (Appendix H).

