8.0 Statistical Considerations

8.1 Methodology

- This is a two-arm randomized non-blinded study whose primary objectives are to compare postoperative pain scores and quality of life (QOL) scores in patients undergoing liver and/or pancreatic resection between those receiving TEA versus IVPCA. Eligible patients will be randomized in a 3:1 allocation ratio to the treatment group of TEA or IVPCA group (to represent our current institutional practice as well as to allow a more accurate determination of overall TEA failures and complications). Randomization will be stratified by the resection type (liver or pancreatic - 1:1). The randomization will be conducted by the CORE prior to surgery and after consent and registration. Pain will be assessed using a numeric/visual pain score at various timepoints. The pain scores will be averaged for each patient and be compared between TEA and IVPCA groups at specific time points as follows: pain scores for the first 6 hours after surgery, pain scores for the next 18hrs after surgery, pain scores for each subsequent 24hr period after surgery until postoperative day #5 or epidural removed, whichever occurs first. QOL will be assessed pre- and postoperatively using SF-8 and SF-36v2. These validated instruments will score 8 domains that will be reduced to two summary measures scales, Physical Component Summary (PCS) and the Mental Health Component Summary (MCS). Scoring will be performed utilizing proprietary certified scoring software from the vendor. QOL scores will be calculated and compared between the two groups of patients.
- Categorical data will be tabulated with frequency and percentages, and continuous variables will be summarized using descriptive statistics mean, standard deviation, median and range. The primary

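### The SF-8 and SF-36v2 baselines are tied only to surgery, so in this non-blinded trial they may be collected after the patient knows the arm or, in TEA, after the epidural is in

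*Combined protocol and SAP*

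**What the plan says.** Section 7.1.2 lists quality of life under the primary endpoints and sets two baselines. For the short form: "Patients will complete a validated SF-8, Acute Recall QOL survey (preoperatively and then at approximately 24hrs after surgery". For the long form: "Patients will complete a validated SF-36v2, Acute Recall QOL survey (preoperatively and then prior to discharge or at approximately 1 week after surgery". The statistics section adds no further timing rule: "QOL will be assessed pre- and postoperatively using SF-8 and SF-36v2".

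Three other events share the preoperative period or border on it:

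- **Allocation (8.1):** "The randomization will be conducted by the CORE prior to surgery and after consent and registration". The same section states: "This is a two-arm randomized non-blinded study".
- **Epidural insertion, TEA arm only (4.2.1):** "All patients assigned to TEA will have thoracic epidurals placed preoperatively in either the holding area or in the operating room". It continues: "All epidural catheters will be tested for correct placement and level of block documented". The first epidural dose that the section states is given after induction of anaesthesia.
- **Baseline immune sample (5.2.2), optional:** "15cc of blood will be drawn intraoperatively prior to anesthesia induction". The section adds that the correlative samples need no extra venepuncture, because they are taken with routine perioperative bloods.

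The baseline is used. Section 8.1 plans a chi-square comparison between arms of the pre-to-postoperative changes in QOL items.

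**The concern.** A baseline should be a measurement that the allocated treatment cannot have influenced. Randomisation gives that protection to anything recorded before allocation. A self-report recorded afterwards, by a patient who knows the arm, does not have it. Here the patient may know whether an epidural is coming and, in one arm only, may already have had a thoracic needle procedure. Both instruments are acute-recall versions, and 8.1 reduces them to a physical and a mental summary, so it is plausible that either event could affect the answers.

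At stake is the change comparison. If the baseline differs between arms because of allocation, a difference in change appears that has nothing to do with postoperative recovery. It could not be separated out later, because no section asks for the survey time to be recorded relative to allocation or insertion.

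**Working it through.** **1. Order of events**

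| Event | Section | Anchor | Stated order relative to randomisation | Stated order relative to epidural insertion |
|---|---|---|---|---|
| SF-8 baseline | 7.1.2 | before surgery | none | none |
| SF-36v2 baseline | 7.1.2 | before surgery | none | none |
| Randomisation | 8.1 | after consent and registration, before surgery | – | before it, since insertion depends on the arm |
| TEA catheter | 4.2.1 | before surgery, holding area or operating room | after | – |
| Immune sample | 5.2.2 | intraoperative, before induction | after, because randomisation precedes surgery | none |
| First stated epidural dose | 4.2.1 | after induction | after | after |

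For the surveys, the sequence consent, randomisation, catheter, survey, surgery satisfies every stated rule. So does consent, survey, randomisation, catheter, surgery. The plan permits the first sequence without prescribing it.

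For the blood, the draw precedes induction and the first stated dose follows it, so the sample precedes that dose. With a holding-area catheter and a draw in the operating room, the sample follows insertion. The order of the draw relative to the placement test, and the agent used for the test, are not stated.

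**2. The plan's own QOL figure**

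Inputs from 8.2: 105 TEA and 35 IVPCA evaluable patients, difference 10, SD 9, two-sided alpha 0.05.

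- Standard error = 9 × √(1/105 + 1/35) = 9 × √0.0381 = 1.757.
- Noncentrality = 10 / 1.757 = 5.69.
- Power (noncentral t, 138 df) = 99.99%, consistent with the stated 99%.

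Baseline timing changes neither the sample size nor this power.

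**3. How a shift would carry through**

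Let b be the difference between arms in mean baseline score caused by allocation or insertion. It depends on how many patients in each arm complete the form late and how far their answers move. If both arms moved equally, b would be 0.

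Difference in mean change = true difference − b.

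The documents give no value for b. The table below is an illustration that takes the SD of 9 in 8.2 as the SD of a change score, which is an assumption. It uses a two-sample t-test with 138 df.

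| Assumed b (points) | b / 1.757 | Chance of a significant result with no true effect | Power for a true 10 if b works against it |
|---|---|---|---|
| 0 | 0 | 5% (nominal) | 99.99% |
| 1 | 0.57 | 8.7% | 99.9% |
| 2 | 1.14 | 20% | 99.5% |
| 3 | 1.71 | 40% | 97.7% |

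A true effect as large as the planned 10 points would still be found. The exposure is a false or distorted difference when the true effect is small or absent. The change comparison in 8.1 is a chi-square test on items, so these percentages show the mechanism and do not estimate the error rate of that test.

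**The case against.** **The fault is permitted, not prescribed.** Preoperative completion is equally compatible with filling in the forms at consent, and nothing shows that they are handed out in the holding area. This stands. It limits the point to what the plan allows, and it leaves a compliant but vulnerable baseline possible.

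**The size is unknown, and not every QOL analysis uses the baseline.** This also stands. The t-test on QOL score in 8.2 mentions no baseline adjustment, and a comparison of postoperative scores alone is untouched. Only the pre-to-post comparison in 8.1 is exposed.

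**A reader might infer that the immune baseline is contaminated by the epidural in every TEA patient with a holding-area catheter.** The documents do not support that, for three reasons:

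- The sample precedes the first stated epidural dose. What may come before it is insertion and an unspecified test.
- Section 2.3 describes attenuation of the neuroendocrine response and better-preserved NK activity with regional techniques. It does not say that inserting or testing a catheter alters a sample taken before induction.
- Section 8 names no change-from-baseline or baseline-adjusted analysis for NK activity or cytokines, and the samples are optional and serve a secondary endpoint.

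**Moving the blood draw has a cost.** The documents describe no routine holding-area draw. An earlier sample could need an extra venepuncture, contrary to 5.2.2. This stands and shapes the fix.

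**Conclusion.** The point holds for the QOL baselines. The plan allows SF-8 and SF-36v2 to be completed after allocation is known or, in TEA only, after catheter insertion. A shift arising that way would enter the planned between-arm comparison of pre-to-postoperative changes. Its size and direction cannot be taken from the documents, and zero is possible. The 48-hour pain AUC is unaffected.

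For the immune sample, only a lesser point holds: its order relative to catheter insertion and test is not fixed and can differ between arms. The documents do not show that this biases any planned analysis.

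This is a cheap improvement worth making, not a threat to the trial's main pain result. It assumes that patients can learn their arm before surgery, which follows from the non-blinded design and preoperative randomisation. It also assumes that no ordering rule stands in the parts not available for this review (the opening pages and the survey appendices).

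**What to change.** **Section 7.1.2:** for both SF-8 and SF-36v2, replace the word *preoperatively* with *after consent and before randomisation*. Consent and registration already precede randomisation in 8.1, so the slot exists. The forms, sample size and power do not change. The cost is that both forms must be finished before the CORE randomises.

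**Section 5.2.2:** record the time of the baseline immune draw relative to epidural insertion and placement test. Draw before insertion only where this coincides with a routine draw, so that the commitment to no additional blood draws still holds. The cost is one recorded time per event. No treatment step changes.
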